Exploratory Obj 1	Pyrexia ³	Medical claim with an ICD-10 code in the inpatient, non-IP, or pharmacy setting for pyrexia (dichotomous)	Index date to end of follow-up, where follow-up will be based on last dose of elranatamab or teclistamab (e.g., 14 days after last recorded dose or 90 days after last recorded dose).
Exploratory Obj 1	Hypotension ³	Medical claim with an ICD-10 code in the inpatient, non-IP, or pharmacy setting for hypotension (dichotomous)	Index date to end of follow-up, where follow-up will be based on last dose of elranatamab or teclistamab (e.g., 14 days after last recorded dose or 90 days after last recorded dose).

	T		
Exploratory Obj 1	Fatigue ³	Medical claim with an ICD-10 code in the inpatient, non-IP, or pharmacy setting for fatigue (dichotomous)	Index date to end of follow-up, where follow-up will be based on last dose of elranatamab or teclistamab (e.g., 14 days after last recorded dose or 90 days after last recorded dose).
Exploratory Obj 1	Nausea or vomiting ³	Medical claim with an ICD-10 code in the inpatient, non-IP, or pharmacy setting for nausea or vomiting (dichotomous)	Index date to end of follow-up, where follow-up will be based on last dose of elranatamab or teclistamab (e.g., 14 days after last recorded dose or 90 days after last recorded dose).
Exploratory Obj 1	Diarrhea ³	Medical claim with an ICD-10 code in the inpatient, non-IP, or pharmacy setting for diarrhea (dichotomous)	Index date to end of follow-up, where follow-up will be based on last dose of elranatamab or teclistamab (e.g., 14 days after last recorded dose or 90 days after last recorded dose).
Exploratory Obj 1	Rash ³	Medical claim with an ICD-10 code in the inpatient, non-IP, or pharmacy setting for rash (dichotomous)	Index date to end of follow-up, where follow-up will be based on last dose of elranatamab or teclistamab (e.g., 14 days after last recorded dose or 90 days after last recorded dose).
Exploratory Obj 1	Angioedema ³	Medical claim with an ICD-10 code in the inpatient, non-IP, or pharmacy setting for angioedema (dichotomous)	Index date to end of follow-up, where follow-up will be based on last dose of elranatamab or teclistamab (e.g., 14 days after last recorded dose or 90 days after last recorded dose).
Exploratory Obj 1	Erythema ³	Medical claim with an ICD-10 code in the inpatient, non-IP, or pharmacy setting for erythema (dichotomous)	Index date to end of follow-up, where follow- up will be based on last

	1	Т	

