Exploratory Obj 1	Other infectious hepatitis ²	Medical claim with an ICD-10 code in the inpatient, non-IP or pharmacy setting for infectious hepatitis (other than hepatitis B or C) (dichotomous)	Index date to end of follow-up, where follow-up will be based on last dose of elranatamab or teclistamab (e.g., 14 days after last recorded dose or 90 days after last recorded dose).
Exploratory Obj 1	Helicobacter pylori ²	Medical claim with an ICD-10 code in the inpatient, non-IP or pharmacy setting for helicobacter pylori (dichotomous)	Index date to end of follow-up, where follow-up will be based on last dose of elranatamab or teclistamab (e.g., 14 days after last recorded dose or 90 days after last recorded dose).

Exploratory Obj 1	Candida esophagitis ²	Medical claim with an ICD-10 code in the inpatient, non-IP or pharmacy setting for candida esophagitis (dichotomous)	Index date to end of follow-up, where follow-up will be based on last dose of elranatamab or teclistamab (e.g., 14 days after last recorded dose or 90 days after last recorded dose).				
Exploratory Obj 1	Urinary tract infection ²	Medical claim with an ICD-10 code in the inpatient, non-IP or pharmacy setting for a urinary tract infection (dichotomous)	Index date to end of follow-up, where follow-up will be based on last dose of elranatamab or teclistamab (e.g., 14 days after last recorded dose or 90 days after last recorded dose).				
Exploratory Obj 1	Time to infection onset	Time in days from index date to first infection for the following infections:	Index date until censor				
Effectiveness	Effectiveness						
Exploratory Obj 2	os	Time (in months) from index date until date of death (continuous)	Index date until censor				
Exploratory Obj 2	TTNT/D	Time (in months) from index date until the date of the next treatment (CAR-T, BsABs, bendamustine or belantamab) or death (continuous)	Index date until censor				

- 1. Variable will be measured as incident and prevalent. Incident cases have 30-day washout period applied
- 2. Variable will be measured as incident and prevalent. Incident cases have 60-day washout period applied
- 3. Variable will be measured as incident and prevalent. Incident cases have 14-day washout period applied

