9.7.6. Tolerability

The prevalence and incidence for each adverse event (Table 3) will be estimated. All prevalence and incidence estimates will be reported as a percent with corresponding 95% CIs.

Prevalance =
$$(\frac{No.\ of\ patients\ with\ an\ event}{Total\ number\ of\ patients\ in\ the\ cohort})\ x\ 100$$

For the incidence analysis, only patients who did not have the event prior to their index date will be included. The length of the washout is dependent on the outcome (see Table 3).

$$Incidence = \left(\frac{\text{No. of patients with an event that did not have an event in baseline}}{\text{Total number of patients in the cohort}}\right) x \ 100$$

PFIZER CONFIDENTIAL

Patients will be assessed over two time periods: from the index date until 14 days or 90 days after their last administration of the index medication.

Additionally, the time to infection onset will be assessed using unadjusted Kaplan-Meier methods. The median time to event in days will be reported along with the IQR. The 95% CIs for the median time to event will be calculated using log-log transformation.

Patients will be censored at the earliest of death, next treatment (CAR-T, BsABs, bendamustine or belantamab), the end of part A or B continuous closed-claim coverage, or the end of data.

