Rash	Adverse events	Claims data	ICD-10 Diagnosis: R21, D72.12
Angioedema	Adverse events	Claims data	ICD-10 Diagnosis: T78.3X, D72.118
Erythema	Adverse events	Claims data	ICD-10 Diagnosis: L53.0, L53.1, L53.2, L51, L52, L71.0, L71.1, L71.8, L93.0, L93.2, L49.0, L49.1, L49.2, L49.3, L49.4, L49.5, L49.6, L49.7, L49.8, L49.9, L00, L26, L30.4, L53.8, L92.0, L95.1, L98.2, L53.9
Muscle spasms	Adverse events	Claims data	ICD-10 Diagnosis: M62.83X
Musculoskeletal pain	Adverse events	Claims data	ICD-10 Diagnosis: M25.50, M25.522, M25.551, M25.552, M25.561, M25.562, M25.572, M25.579, M25.59, M25.612, M25.621, M25.629, M25.631, M25.641, M25.642, M25.662, M25.669, M25.671, M25.673, M25.674, M25.675, M25.676, M54.6, M54.81, M79.1, M79.12, M79.18, M79.621, M79.622, M79.631, M79.639, M79.641, M79.644, M79.646, M79.669, M79.671, M79.673, M79.675, M25.511, M25.512, M25.519, M25.521, M25.529, M25.531, M25.532, M25.539, M25.541, M25.542, M25.549, M25.611, M25.619, M25.622, M25.632, M25.639, M25.649, M25.651, M25.659, M25.672, M25.69, M25.671, M25.69, M25.672, M25.69, M25.672, M25.69, M25.672, M27.69, M27.603, M79.604, M79.605, M79.606, M79.609, M79.629, M79.632, M79.672, M79.674, M79.676
COVID-19	Adverse event - infection	Claims data	ICD-10 Diagnosis: U07. 1

COVID-19 pneumonia	Adverse event -	Claims	ICD-10: J12.82
Adenoviral pneumonia	infection Adverse event - infection	data Claims data	ICD-10 Diagnosis: J12.0
Cytomegaloviral pneumonitis	Adverse event - infection	Claims data	ICD-10 Diagnosis: B25.0
Other pneumonia	Adverse event - infection	Claims data	ICD-10 Diagnosis: A01.03, A02.22, A20.2, A21.2, A31.0, A37.01, A37.11, A37.81, A37.91, A43.0, A48.1, B01.2, B05.2, B06.81, B37.1, B38.0, B38.2, B39.0, B39.2, B58.3, B59, B77.81, J10.00, J10.08, J11.00, J11.08, J12.1, J12.2, J12.3, J12.81, J12.89, J12.9, J13, J14, J15.0, J15.1, J15.20, J15.211, J15.212, J15.29, J15.3, J15.4, J15.5, J15.6, J15.7, J15.8, J15.9, J16.0, J16.8, J17, J18.0, J18.1, J18.8, J18.9, J85.1
Upper respiratory tract infection	Adverse event - infection	Claims data	ICD-10 Diagnosis: J20.9, J00.0, J04.0, J06.0, J06.9, J02.9
Sepsis	Adverse event - infection	Claims data	ICD-10 Diagnosis: A02.1, A32.1, A40.7, A40.0, A40.1, A40.3, A40.8, A41.9, A41.01, A41.02, A41.1, A41.2, A41.3, A41.4, A41.50, A41.51, A41.52, A41.53, A41.59, A41.81, A41.89, A42.9, A54.7, B37.86, R65.7, R65.20, A22.21, A26.7, A41.7, A41., A41.0, A41.5, P36.8, P36.0, P36.10, P36.19, P36.2, P36.30, P36.39, P36.4, P36.5, P36.8

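### The Rash code list has no drug-eruption codes (L27.x), and the Erythema list counts rosacea-group and cutaneous lupus codes that a 14-day washout will not reliably remove.

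*Protocol*

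**What the plan says.** Annex 2 gives the Rash row as "ICD-10 Diagnosis: R21, D72.12". The Erythema row opens with "L53.0, L53.1, L53.2, L51, L52, L71.0, L71.1, L71.8, L93.0, L93.2", continues with L49.0 to L49.9, and closes with "L00, L26, L30.4, L53.8, L92.0, L95.1, L98.2, L53.9".

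Section 9.3, Table 3, makes both outcomes dichotomous: a medical claim carrying a listed code is enough. Footnote 3 of that table covers both and says "Incident cases have 14-day washout period applied". Section 9.7.6 reports prevalence and incidence for each event as percentages with 95% confidence intervals. Prevalence counts every patient with an event. For incidence, "only patients who did not have the event prior to their index date will be included", and the washout length is taken from Table 3.

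Section 9.8 says that outcomes are coded from the lists in the protocol and that the protocol is to be adhered to in the analysis. The Annex 2 rows are therefore the working definitions of these outcomes.

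**The concern.** An outcome code list can fail by leaving out the code that a clinician would use for the event, or by taking in codes for something else. Here each list shows one of these faults.

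Rash omits L27, the ICD-10 family for skin eruption due to substances taken internally. A patient whose only skin claim carries L27.0 or L27.1 is recorded as having no rash.

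Erythema includes codes from the rosacea group (L71) and the cutaneous lupus group (L93). These conditions are usually long-standing, and a routine visit claim after index would be enough to record an adverse event. A short look-back does little to screen out a condition that is claimed only now and then.

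At stake are two percentages under Exploratory Objective 1, in a study that the protocol designates a PASS. The confidence intervals reflect sampling error only and would not reveal either problem.

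**Working it through.** **Inputs.** Rash and Erythema rows: Annex 2. Any-claim rule and 14-day washout: Section 9.3, Table 3 and footnote 3. Prevalence and incidence rules: Section 9.7.6. Patients with an elranatamab claim as of August 2024: 133, Section 9.5. The plan states no figure on this point, so there is none to reproduce.

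**Step 1: which codes are listed.** The two rows were searched by code prefix (2 codes in Rash, 28 in Erythema).

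| Prefix | Matches | Codes | Row |
|---|---|---|---|
| L27 | 0 | none | neither |
| L71 | 3 | L71.0, L71.1, L71.8 | Erythema |
| L93 | 2 | L93.0, L93.2 | Erythema |
| L53 | 5 | L53.0, L53.1, L53.2, L53.8, L53.9 | Erythema |
| L51 | 1 | L51 (no wildcard) | Erythema |
| R21 | 1 | R21 | Rash |
| D72.12 | 1 | D72.12 | Rash |

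**Step 2: can chronic disease reach the Erythema count?** For prevalence it can, because any listed claim in the assessment window counts and there is no baseline condition. For incidence it can whenever no listed code was claimed in the 14 days before index. The Section 9.7.6 sentence on prior events could be read as an unlimited look-back, but the sentence after it ties the length to Table 3, which gives 14 days.

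**Step 3: how weak is a 14-day washout?** This step is an illustration on an assumption that is not in the documents: a chronic skin condition is claimed once every 90 to 180 days, at times unrelated to the index date.

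- Chance of a claim inside the washout = 14 / interval.
- Every 90 days: 14/90 = 15.6%, so 84.4% pass the washout.
- Every 180 days: 14/180 = 7.8%, so 92.2% pass.

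On that assumption most such patients would be eligible as incident cases, and a later claim would count as a new event.

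**Step 4: scale of one misclassified patient.** Change in prevalence = 100 × k / 133.

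- k = 1: 0.75 points
- k = 2: 1.5 points
- k = 5: 3.8 points
- k = 10: 7.5 points

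The value of k is unknown. The 133 is a count before eligibility criteria and before the study period was extended, so it is not the analysis denominator. With a larger cohort each patient would count for less.

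**The case against.** **Drug rash is still partly captured.** A reader might infer that the plan misses drug rash altogether. It does not. R21 takes in rash whatever its cause, D72.12 is itself a drug-rash code (with eosinophilia and systemic symptoms), and L53.0 (toxic erythema) and L51 (erythema multiforme group) are under Erythema. Only patients whose eruption is coded solely as L27.x, or under another unlisted code, are lost. This stands and limits the Rash half of the point.

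**Attribution is not claimed.** Table 3 asks for a claim for rash or erythema, not a drug-attributed event, and Section 11 says product and event cannot be linked for an individual. This stands, so the test is whether a code describes the named event. L27 does describe a rash. Rosacea and cutaneous lupus are separate diseases and poor proxies for erythema as an adverse event.

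**The whole Erythema list is not at fault.** A reader might infer that the row is mainly unrelated disease. Several other entries are erythematous or potentially drug-related, and the L71 and L93 families are only partly listed (no L71.9, no L93.1). That does not justify cutting the row to L53.x, which would also drop L52 and the ten L49 codes without a reason.

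**L51.** A reader might infer that severe skin reactions are hidden under Erythema. That needs prefix matching. Under exact matching the bare L51 would not pull in its subcodes. The protocol does not say which rule applies, and bare codes appear elsewhere in Annex 2 (C50, for example), so this is a notation query only.

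**Acknowledged limitations.** Section 9.9 concedes that diagnosis codes may not capture every event. That covers under-capture in general terms, but not over-inclusion by the protocol's own list.

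**Conclusion.** The point holds in a limited form. As written, Annex 2 leaves eruptions coded only as L27.x out of Rash and lets rosacea-group and cutaneous lupus claims count as Erythema. The first error can only lower the Rash percentage and the second can only raise the Erythema percentage.

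Neither size can be calculated, because the documents give no frequency for these codes. A reader might infer that the percentages are wrong by several points, or that a count is pushed past the CMS display limit for small cells. The documents support neither.

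The effect is confined to two exploratory outcomes that are described without comparison between cohorts. No primary objective depends on them. Exploratory Objective 3 repeats all objectives for teclistamab, so the same lists apply to that cohort.

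The presence or absence of each code can be checked in Annex 2. What the codes mean is taken from the ICD-10 classification that the protocol uses; the protocol prints no labels for them.

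**What to change.** Amend two rows of Annex 2:

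- Rash: add L27.0 and L27.1 to R21 and D72.12.
- Erythema: delete L71.0, L71.1, L71.8, L93.0 and L93.2.
- Erythema: print L51 as L51.x if the whole family is meant.

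If the sponsor prefers to keep the lists, a sentence justifying the absence of L27.x and the presence of L71 and L93 would let readers interpret the two percentages.

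The cost is a short amendment and a re-run of two outcomes in each cohort. V2.0 already changed Annex 2 code lists (anti-infective codes added, one daratumumab code corrected), so there is a precedent. The drawback is that final Rash and Erythema results will not be comparable with interim results produced under the present lists. Either re-run those two outcomes on the interim data cuts or note the change in the final report.

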Exploratory Obj 1	Hypogammaglobuli nemia ¹	Medical claim with an ICD-10 code in the inpatient, non-IP, or pharmacy setting for hypogammaglobulinemia (dichotomous)	Index date to end of follow-up, where follow-up will be based on last dose of elranatamab or teclistamab (e.g., 14 days after last recorded dose or 90 days after last recorded dose).
Exploratory Obj 1	Hypophosphataemia	Medical claim with an ICD-10 code in the inpatient, non-IP, or pharmacy setting for hypophosphatemia (dichotomous)	Index date to end of follow-up, where follow-up will be based on last dose of elranatamab or teclistamab (e.g., 14 days after last recorded dose or 90 days after last recorded dose).
Exploratory Obj 1	Hypokalaemia ¹	Medical claim with an ICD-10 code in the inpatient, non-IP, or pharmacy setting for hypokalemia (dichotomous)	Index date to end of follow-up, where follow-up will be based on last dose of elranatamab or teclistamab (e.g., 14 days after last recorded dose or 90 days after last recorded dose).
Exploratory Obj 1	Hepatotoxicity ¹	Medical claim with an ICD-10 code in the inpatient, non-IP, or pharmacy setting for hepatotoxicity (dichotomous)	Index date to end of follow-up, where follow- up will be based on last dose of elranatamab or teclistamab (e.g., 14 days after last recorded dose or

			90 days after last recorded dose).
Exploratory Obj 1	Renal failure ²	Medical claim with an ICD-10 code in the inpatient, non-IP, or pharmacy setting for renal failure (dichotomous)	Index date to end of follow-up, where follow-up will be based on last dose of elranatamab or teclistamab (e.g., 14 days after last recorded dose or 90 days after last recorded dose).
Exploratory Obj 1	Peripheral neuropathy ¹	Medical claim with an ICD-10 code in the inpatient, non-IP, or pharmacy setting for peripheral neuropathy (dichotomous)	Index date to end of follow-up, where follow-up will be based on last dose of elranatamab or teclistamab (e.g., 14 days after last recorded dose or 90 days after last recorded dose).
Exploratory Obj 1	Arthralgia ³	Medical claim with an ICD-10 code in the inpatient, non-IP, or pharmacy setting for arthralgia (dichotomous)	Index date to end of follow-up, where follow-up will be based on last dose of elranatamab or teclistamab (e.g., 14 days after last recorded dose or 90 days after last recorded dose).

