			dose of elranatamab or teclistamab (e.g., 14 days after last recorded dose or 90 days after last recorded dose).
Exploratory Obj 1	Muscle spasms ³	Medical claim with an ICD-10 code in the inpatient, non-IP, or pharmacy setting for muscle spasms (dichotomous)	Index date to end of follow-up, where follow-up will be based on last dose of elranatamab or teclistamab (e.g., 14 days after last recorded dose or 90 days after last recorded dose).
Exploratory Obj 1	Musculoskeletal pain ³	Medical claim with an ICD-10 code in the inpatient, non-IP, or pharmacy setting for musculoskeletal pain (dichotomous)	Index date to end of follow-up, where follow-up will be based on last dose of elranatamab or teclistamab (e.g., 14 days after last recorded dose or 90 days after last recorded dose).
Infections			
Exploratory Obj 1	COVID-19 ²	Medical claim with an ICD-10 code in the inpatient, non-IP, or pharmacy setting for COVID-19 (dichotomous)	Index date to end of follow-up, where follow-up will be based on last dose of elranatamab or teclistamab (e.g., 14 days after last recorded dose or 90 days after last recorded dose).
Exploratory Obj 1	Adenoviral pneumonia ²	Medical claim with an ICD-10 code in the inpatient, non-IP, or pharmacy setting for adenoviral pneumonia (dichotomous)	Index date to end of follow-up, where follow-up will be based on last dose of elranatamab or teclistamab (e.g., 14 days after last recorded dose or 90 days after last recorded dose).
Exploratory Obj 1	Cytomegaloviral pneumonitis ²	Medical claim with an ICD-10 code in the inpatient, non-IP, or pharmacy setting for cytomegaloviral pneumonitis (dichotomous)	Index date to end of follow-up, where follow-up will be based on last dose of elranatamab or

			teclistamab (e.g., 14 days after last recorded dose or 90 days after last recorded dose).
Exploratory Obj 1	COVID-19 pneumonia ²	Medical claim with an ICD-10 code in the inpatient, non-IP, or pharmacy setting for COVID-19 related pneumonia (dichotomous)	Index date to end of follow-up, where follow-up will be based on last dose of elranatamab or teclistamab (e.g., 14 days after last recorded dose or 90 days after last recorded dose).

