Use of premedication	Outcome - Dosing and Administration Patterns	Claims data	HCPCS: J1094, J1096, J8540, J1100, J0131, J7637, J7638, J7312, J1200, Q0163 Generic names (and associated NDCs): Acetaminophen, Dexamethasone, Diphenhydramine
Inpatient	Baseline characteristic, Outcome - HCRU	Claims data	Any event in the inpatient table or an event in the non-inpatient table where acute_subacute is "acute inpatient" or where utilization type is "professional services", and service subcategory contains the term "hospital/IP encounter"
Outpatient	Baseline characteristic, Outcome - HCRU	Claims data	Any event in the non-inpatient table where utilization type is outpatient and service subcategory is not "emergency dept encounter"

Emergency department	Baseline characteristic, Outcome - HCRU	Claims data	Any event in the non-inpatient table where utilization type is "outpatient" and service subcategory is "emergency dept encounter"
Cytokine release syndrome (CRS)	Safety events	Claims data	ICD-10 Diagnosis: D89.83x
Immune effector cell- associated neurotoxicity Syndrome (ICANS)	Adverse events	Claims data	ICD-10 Diagnosis: G92.0x
Anemia	Adverse events	Claims data	ICD-10 Diagnosis: D46.0, D46.1, D46.20, D46.21, D46.22, D46.4, D46.9, D46.A, D46.B, D46.C, D46.Z, D47.4, D50.0, D50.1, D50.8, D50.9, D51.0, D51.1, D51.2, D51.3, D51.8, D51.9, D52.0, D52.1, D52.8, D52.9, D53.0, D53.1, D53.2, D53.8, D53.9, D55.0, D55.1, D55.2, D55.21, D55.29, D55.3, D55.8, D55.9, D59.0, D59.1, D59.10, D59.11, D59.12, D59.13, D59.19, D59.2, D59.3, D59.30, D59.31, D59.39, D59.4, D59.5, D59.6, D59.8, D59.9, D60.0, D60.1, D60.8, D60.9, D61.01, D61.09, D61.1, D61.2, D61.3, D61.810, D61.811, D61.818, D61.82, D61.89, D61.9, D63.0, D63.1, D63.8, D64.9, D75.81
Lymphopenia	Adverse events	Claims data	ICD-10 Diagnosis: D72.810
Hypogammaglobulinemia	Adverse events	Claims data	ICD-10 Diagnosis: D80.1, D80.3, D80.9
Hypophosphataemia	Adverse events	Claims data	ICD-10 Diagnosis: E83.39
Hypokalaemia	Adverse events	Claims data	ICD-10 Diagnosis: E87.6
Arthralgia	Adverse events	Claims data	ICD-10 Diagnosis: M25.5x
Pyrexia	Adverse events	Claims data	ICD-10 Diagnosis: R50.x
Hypotension	Adverse events	Claims data	ICD-10 Diagnosis: I95.0, I95.81, I95.89, I95.9, I95.2
Fatigue	Adverse events	Claims data	ICD-10 Diagnosis: R53.x, G93.3x

Nausea or vomiting	Adverse events	Claims data	ICD-10 Diagnosis: R11.x
Diarrhea	Adverse events	Claims data	ICD-10 Diagnosis: R19.7, K59.1

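### The Annex 2 code list for the Musculoskeletal pain adverse event contains 23 joint-stiffness codes (M25.6xx), so patients with only a stiffness claim would be reported as having pain

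*Protocol*

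**What the plan says.** Section 9.3, Table 3, lists Musculoskeletal pain among the Exploratory Objective 1 outcomes: "Medical claim with an ICD-10 code in the inpatient, non-IP, or pharmacy setting for musculoskeletal pain (dichotomous". Footnote 3 gives it a 14-day washout for incident cases. Section 9.3 refers the reader to Annex 2 for the codes.

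The Annex 2 row for this outcome begins with joint-pain codes, "M25.50, M25.522, M25.551, M25.552, M25.561, M25.562, M25.572, M25.579, M25.59", and continues directly with "M25.612, M25.621, M25.629, M25.631, M25.641, M25.642, M25.662, M25.669, M25.671, M25.673, M25.674, M25.675, M25.676". After some M54 and M79 codes it returns to M25.5xx and then gives a second M25.6xx run, "M25.611, M25.619, M25.622, M25.632, M25.639, M25.649, M25.651, M25.659, M25.672, M25.69".

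Arthralgia is a separate outcome in Table 3, with the same washout. Its Annex 2 entry is the whole joint-pain family: "ICD-10 Diagnosis: M25.5x".

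Section 9.7.6 estimates prevalence and incidence for each adverse event separately. Section 9.8 says that measures are coded from the lists in the protocol and that the analysis is to keep to it.

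**The concern.** The outcome is named and defined as pain, but a third of the distinct codes that trigger it denote stiffness. The protocol nowhere says that stiffness is meant to count as pain. Its own Arthralgia row stops at M25.5x and does not reach into M25.6.

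Because Section 9.8 ties the programming to the printed codes, the list would be run as it stands. The reported percentage with musculoskeletal pain would then include patients who have no pain claim at all. The same list serves the teclistamab cohort under Exploratory Objective 3.

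**Working it through.** **Inputs.** The codes printed in the Annex 2 Musculoskeletal pain row, counted once each, and the Arthralgia wildcard M25.5x from the same annex.

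**Count by family (distinct codes).**
- M25.5xx: 9 in the first run ("M25.50, M25.522, M25.551, M25.552, M25.561, M25.562, M25.572, M25.579, M25.59") + 11 in the second ("M25.511, M25.512, M25.519, M25.521, M25.529, M25.531, M25.532, M25.539, M25.541, M25.542, M25.549") = 20
- M25.6xx: 13 in the first run + 10 in the second = 23
- M54: 2
- M79: 23
- M27: 2
- Total: 20 + 23 + 2 + 23 + 2 = 70

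Share of M25.6xx: 23/70 = 0.329, or 33%.

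**Does poor legibility explain it?** No. The first 13 M25.6xx codes form one clean ascending run. The later part of the row repeats some codes and shows two M27 entries, which may be a reading fault. Repeats do not change a distinct count, and the 23 does not depend on the M27 entries.

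**Effect on prevalence.** Let P be the patients with at least one pain code in the window, S those with at least one M25.6xx code, and N the cohort size.
- As written: |P ∪ S| / N
- As defined in Table 3: |P| / N
- Difference: |S without P| / N, which is never negative

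If a share s of the flagged patients have only a stiffness code, the relative overstatement is s/(1 − s). The protocol gives no value for s.

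**Effect on incidence.** The incident cases change in two opposite ways.
- Gained: patients with a stiffness code but no pain code after index, and neither kind in the washout.
- Lost: patients with a pain code after index and no pain code in the washout, but a stiffness code in it.

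The net sign depends on which group is larger, and the protocol does not tell.

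**Relation to Arthralgia.** All 20 M25.5xx codes in the row fall under the Arthralgia wildcard. The row does not cover the whole family: M25.559, M25.569 and M25.571 exist in ICD-10-CM but are not listed. A patient with only one of these has Arthralgia but not Musculoskeletal pain.

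**After deletion of M25.6xx.** 70 − 23 = 47 distinct codes. With the three missing joint-pain codes added, 47 + 3 = 50.

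**The case against.** The protocol prints no titles for its codes, so the meaning of M25.6 comes from ICD-10-CM and not from the document. From the document alone one can say only that these codes lie outside the family it labels Arthralgia. That is true. But ICD-10-CM is the classification in which the protocol writes its outcomes, and its code titles are part of the definition being applied.

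Section 9.9 already warns that diagnosis codes may misclassify events. That warning concerns how providers code. It does not cover a list that selects codes for a different symptom.

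The consequence is small. This is one of many dichotomous events under an exploratory objective, and no formal comparison between groups is planned. That stands, and it limits the weight of the point.

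A reader might go further and infer that the overlap with Arthralgia is itself an error, because one joint-pain claim flags two adverse events. The protocol does not support that. Section 9.7.6 estimates each event on its own, and no planned analysis adds these rows. Joint pain is a kind of musculoskeletal pain, and Table 3 states no exclusion for this outcome, whereas it does for Other pneumonia. Other rows overlap too: B59 is in both Other pneumonia and PJP, and B25.0 is in both cytomegaloviral rows. Each percentage is right under its own definition. Removing M25.5xx would under-capture the outcome.

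**Conclusion.** The point holds for the stiffness codes. The Musculoskeletal pain row contains 23 M25.6xx codes that do not match the outcome as Table 3 defines it. Prevalence can only be raised by them. Incidence can be misclassified in either direction.

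The size is unknown. It would be wrong to read 33% of codes as 33% of patients: a patient is a false case only if a stiffness code appears with no listed pain code in the window. A reader might also try a stiffness-only share of 5% to 20% and obtain an overstatement of 5% to 25% (0.05/0.95 = 0.053; 0.20/0.80 = 0.25). Nothing in the protocol supports that range, and it leaves out shares near zero.

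The conclusion rests on the ICD-10-CM title of M25.6 and on the row as printed. It concerns Exploratory Objective 1 and its teclistamab replication only, and is minor.

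**What to change.** - Delete all M25.6xx codes from the Annex 2 Musculoskeletal pain row. This leaves 47 distinct codes as printed.
- Keep the joint-pain codes, but replace the 20 listed ones by M25.5x, the notation of the Arthralgia row, so that the whole family is covered.
- Check the repeated codes and the two M27 entries against the source list at the same time.
- Footnote the results table: Musculoskeletal pain includes Arthralgia, so the two rates are not independent and must not be added. With the family complete, every prevalent Arthralgia case is also a prevalent Musculoskeletal pain case. The same need not hold for incident cases, since earlier pain at another site can remove a patient from the broader event and not from the narrower one.

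The cost is an edit to one row and a rerun of one outcome in both cohorts. Version 2.0 already corrected Annex 2 codes by amendment, and the final analysis is planned for 27 February 2026. Any interim figure for this outcome produced with the old list would need a note that the definition changed.
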